8.2.2 Primary Analysis - Goal Attainment Scaling

Data Conversion: Individual GAS scores converted to T-scores (M=50, SD=10)

Baseline Comparisons: Independent samples t-tests for GAS T-scores across three domains

Primary Efficacy Analysis: ANCOVA comparing IG1 (weeks 0-7) vs. IG2 (weeks 7-14)

- Covariates: Baseline domain differences, IG2 control period changes
- Combined score calculated by averaging three domain T-scores

Secondary Analysis:

- Within-group paired samples t-tests for intervention effects
- Maintenance analysis for IG1 (weeks 8-14)
- Clinical significance threshold: 10+ T-score point improvements

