4.2 Study Design Overview

- Phase 1: Intervention Group 1 (IG1) receives BRP intervention for 7 weeks while Intervention Group 2 (IG2) receives standard care (waitlist control)
- Phase 2: IG2 receives BRP intervention for 7 weeks while IG1 continues standard care activities
- Total study duration: 14 weeks

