7.1.2 Goal Attainment Scaling (GAS)

Domains: Three individualized goals per participant

- Behavior
- Engagement/Participation
- Resilience

Scoring: -2 (much worse than expected) to +2 (much better than expected outcome) **Frequency:**

Weekly observations during both intervention and control periods **Conversion:** Raw scores converted to T-scores (M=50, SD=10) for statistical analysis

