8.2 Statistical Methods

8.2.1 Primary Analysis - Standardized Measures

Baseline Comparisons: Independent samples t-tests for continuous variables to assess randomization success

Primary Efficacy Analysis: Analysis of Covariance (ANCOVA)

- Independent Variable: Group assignment (IG1 intervention vs. IG2 waitlist control)
- Dependent Variables: Week 7 standardized assessment scores
- Covariates: Baseline scores, any maturation effects identified in IG2 waitlist period
- Effect sizes: Cohen's d with 95% confidence intervals

Secondary Analysis: Paired samples t-tests for within-group changes

- One-tailed tests for intervention effects (directional hypotheses)
- Two-tailed tests for control period effects

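### The primary GAS efficacy test compares BRP with BRP, so it cannot show that the programme works

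*Combined protocol and SAP*

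**What the plan says.** Section 4.2 sets the phases. In Phase 1, "Intervention Group 1 (IG1) receives BRP intervention for 7 weeks while Intervention Group 2 (IG2) receives standard care (waitlist control"). In Phase 2, "IG2 receives BRP intervention for 7 weeks while IG1 continues standard care activities".

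Section 8.2.2 defines the main GAS test as "Primary Efficacy Analysis: ANCOVA comparing IG1 (weeks 0-7) vs. IG2 (weeks 7-14"), and adds "Covariates: Baseline domain differences, IG2 control period changes". The other GAS outcome analyses in that section are paired within-group tests, a maintenance analysis for IG1 and a 10-point threshold for clinical significance. None compares BRP with the concurrent waitlist period.

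For the standardized measures, section 8.2.1 takes a different contrast at week 7: "Independent Variable: Group assignment (IG1 intervention vs. IG2 waitlist control"). Section 7.1.2 says GAS is scored through "Weekly observations during both intervention and control periods", and the schedule in section 7.2 shows an initial GAS at week 0 and weekly GAS in both groups.

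**The concern.** Read against section 4.2, both windows in the GAS test are BRP windows: IG1's first seven weeks and IG2's last seven. The difference between them is not an estimate of what BRP does. A programme that works equally well in both groups should give a null result. A significant result would point to a difference in period, age, order or group.

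GAS is listed among the primary outcome measures (section 7.1), and section 2.2 names it as a measure of child improvement. Without a controlled GAS comparison, the GAS evidence reduces to uncontrolled change over time on goals scored by the research team (section 9.1), with no masking described. It also gives up what section 6.2 says the control activities are for, namely to account for the effect of positive contact with researchers. A null result could be misread as failure, or as equal benefit in both groups; neither reading would be supported.

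**Working it through.** The plan gives no GAS power, sample size or effect size, so there is no GAS figure to reproduce. The check is of the contrast itself.

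**Step 1. Match windows to conditions (sections 4.2 and 8.2.2).**

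| Group | Weeks 0-7 | Weeks 7-14 |
|---|---|---|
| IG1 | BRP (used in GAS test) | Standard care |
| IG2 | Waitlist control | BRP (used in GAS test) |

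**Step 2. Expected difference in change.** Let E be the BRP effect, and m1 and m2 the changes that would occur anyway in the two periods.

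- Planned: (E + m1) − (E + m2) = m1 − m2. E cancels.
- Concurrent, weeks 0-7: (E + m1) − m1 = E.

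**Step 3. Can the covariates restore a control?** No, for two reasons.

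- IG2's control-period change does not exist for IG1. Entered as a group constant (c for IG2, 0 for IG1), it equals c × (1 − group). With the intercept and group it gives three columns of rank 2, so the group effect cannot be estimated.
- However it is coded, both covariates are measured before BRP starts. A common E is then added to every outcome in the model, and the intercept absorbs it. The group coefficient and its p-value are the same whatever E is.

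**Step 4. Size, by simulation (4,000 trials per setting).** From the plan: T-score SD 10 (section 8.2.2) and alpha 0.05 (section 8.4). Group sizes: 9 per group, the middle of the 8-10 in section 8.3, and 16 per group, from the 32 children in section 5.2 (32 / 2). Assumed: two-sided test, correlation 0.5 between time points, equal BRP effect in both groups, no trend, and each group adjusted for its own pre-BRP score.

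| True effect (T-points) | Planned, 9 per group | Concurrent, 9 per group | Planned, 16 per group | Concurrent, 16 per group |
|---|---|---|---|---|
| 0 | 5.0% | 5.2% | 4.9% | 4.4% |
| 5 | 5.0% | 19.5% | 4.9% | 34.6% |
| 10 | 4.9% | 60.5% | 5.2% | 86.9% |
| 20 | 5.1% | 99.2% | 5.8% | 100% |

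Entries are rejection rates. Differences within the planned columns are simulation noise. The planned contrast's mean estimate stays near 0 throughout; at a 10-point effect the concurrent contrast's mean estimate is 10.0.

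**Step 5. Effect of a trend.** Suppose both groups drift up 3 points per phase. IG1 ends at 53 + E from a baseline of 50. IG2 ends at 56 + E, from 53 if its baseline is week 7 or from 50 if it is week 0. With an ANCOVA slope of 0.5:

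- Week-7 baseline for IG2: (53 − 56) − 0.5 × (50 − 53) = −1.5 points; rejection 6-7%.
- Week-0 baseline for IG2: (53 − 56) − 0.5 × (50 − 50) = −3 points; rejection about 10% at 9 per group.

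Section 8.2.2 does not say which baseline is meant.

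**The case against.** The strongest reply is that the plan does bring control-period information into the model, through the covariate for IG2's control-period change, so a model without it is simpler than the one written. That is a fair description of the text, but step 3 shows that the covariate cannot turn a comparison of two BRP periods into BRP versus control.

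Four further points deserve weight.

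- **Scope.** Objective 1 is also tested by the concurrent ANCOVA on the standardized measures (section 8.2.1), so the trial keeps randomised evidence. Objective 2 and the child hypothesis in section 2.2 are worded as change by the end of the intervention, which the within-group GAS tests address. This stands: the defect lies in the GAS efficacy contrast, not in the whole trial.
- **Cost.** Sections 5.2, 8.1 and 8.3 already report achieved numbers, observed power and effect sizes. Outcome data have apparently been examined, so a new primary contrast is not a prespecified one. This stands and is reflected in the fix.
- **Power inputs.** No GAS sample size, correlation or observed SD is given. For a 10-point effect, correlations of 0.2-0.7 and SDs of 7-13 move concurrent power from 33% to 96% at 9 per group, and from 56% to 100% at 16. This stands for the power figures; the cancellation of E does not depend on them.
- **The replacement.** Classroom terms use three degrees of freedom, although in a rerun they cost only about 1 percentage point of power. Scoring by the research team affects the concurrent contrast too, and the change does not remove that weakness.

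**Conclusion.** The concern holds, for GAS only. As written, the primary GAS efficacy test has power equal to alpha, about 5%, for any BRP effect common to both groups. This is algebra, resting on an additive effect of equal size in IG1 and IG2. If the effects differ, the test detects that difference, which is still not efficacy. The concurrent contrast would have roughly 60% power at 9 per group and 87% at 16 for a 10-point effect, with SD 10 and correlation 0.5 assumed; these figures are illustrative. No other GAS analysis in the plan supplies a controlled comparison, so the contrast must be changed before any efficacy statement is made from GAS.

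**What to change.** In section 8.2.2, replace the primary efficacy contrast with: ANCOVA of the week-7 GAS T-score, IG1 (BRP, weeks 0-7) versus IG2 (control, weeks 0-7), adjusted for the child's own week-0 GAS T-score and for classroom. Classroom belongs in the model because randomisation was within classroom (section 4.3). Delete the covariate for IG2's control-period change; those data now form the control arm.

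Keep IG1 weeks 0-7 versus IG2 weeks 7-14 as a secondary check that the response to BRP is similar in the two groups, state which week is IG2's baseline, and do not call it efficacy.

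No new data are needed, since sections 7.1.2 and 7.2 already schedule week-0 and weekly GAS in both groups. The cost is a SAP amendment and a re-analysis. Date the amendment, and report the change as made after data collection, which limits how confirmatory the GAS result can be.

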8.3 Missing Data Handling

Approach: Listwise deletion for each analysis **Rationale:** Participants included only with complete baseline and outcome data for each specific measure **Impact:** Sample sizes range from n=17-19 for primary ANCOVA analyses (8-10 participants per group)

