5.2 Sample Size

Target enrollment: n=40 participants (based on total ELC enrollment) Achieved enrollment: n=38 participants Final analytic sample: n=32 participants with complete assessments

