7.2 Data Collection Schedule

Assessment Period	IG1	IG2	Measures
Baseline (Week 0)	X	X	All standardized measures, initial GAS
Week 6/7	X	X	All standardized measures
Week 14	X	X	All standardized measures
Weekly	X	X	GAS observations

8. Statistical Analysis Plan

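### Listwise deletion in the week-7 ANCOVA drops children who have a week-7 score but no baseline form and makes no use of week-14 scores; using these data can reduce the standard error, by an amount the documents do not let us fix

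*Combined protocol and SAP*

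**What the plan says.** Section 8.3 (Missing Data Handling) of the combined protocol and SAP states "Approach: Listwise deletion for each analysis". The text given as its rationale is "Participants included only with complete baseline and outcome data for each specific measure", which describes the rule without giving a reason for it. The same section puts the primary ANCOVAs at 17 to 19 children, 8 to 10 per group.

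Section 8.2.1 sets the outcome as "Dependent Variables: Week 7 standardized assessment scores" and lists "Covariates: Baseline scores, any maturation effects identified in IG2 waitlist period". Section 7.2 schedules the battery three times in both groups: "All standardized measures, initial GAS" at baseline, then "All standardized measures" at week 6/7 and again at week 14. Section 5.2 reports "Achieved enrollment: n=38 participants Final analytic sample: n=32 participants with complete assessments".

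The plan has no imputation, no repeated-measures model and no sensitivity analysis for missing data. It gives no count of forms missing by visit.

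**The concern.** Two kinds of collected data are set aside. A child whose week-7 outcome was observed leaves the analysis because a covariate is absent, although randomisation alone makes that outcome informative about the group difference. A child with baseline and week-14 scores but no week-7 form contributes nothing, although those two scores predict the missing one.

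What is at stake is precision. Enrolment was capped by the size of the centre, and 8.1 itself reports observed power below 20% for the standardised measures. Better use of forms already returned is one of the few remedies left. The point concerns the estimator for the standardised measures. It does not concern the GAS ANCOVA in 8.2.2, which compares different periods.

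**Working it through.** **The plan's counts.** Enrolled: 38 (5.2). In the primary ANCOVA: 17–19 (8.3). Left out: 38 − 19 = 19 to 38 − 17 = 21. The documents do not say how many of these lack baseline, week 7 or both.

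**Assumed inputs.** n = 9 complete children per arm, the middle of 8–10. Equal correlation r = 0.6 between any two visits, range 0.3–0.7. The documents state no correlation. The group sizes in 8.1 (21, 25 and 35 for d = 0.68, 0.63 and 0.53) are reproduced by the two-sided ANCOVA formula 2(1.960 + 0.842)²(1 − r²)/d² with r = 0.62, which gives 20.9, 24.3 and 34.4 before rounding up. That is compatible with r near 0.6 but does not show that this is how they were obtained.

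**(a) m further children per arm with week 7 but no baseline.** The ratio of the standard error in a baseline-constrained model to that in complete-case ANCOVA is √{[n/(1 − r²)] / [n/(1 − r²) + m]}. Here n/(1 − r²) = 9/0.64 = 14.06.
- m = 2: √(14.06/16.06) = 0.936, a reduction of about 6%.
- m = 5: √(14.06/19.06) = 0.859, about 14%. Over r = 0.3–0.7 the ratio runs from 0.815 to 0.883.
- m = 10: √(14.06/24.06) = 0.764, about 24%.

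**(b) m further children per arm with baseline and week 14 but no week 7.** The ratio is √{n[p²/(n + m) + (1 − p²)/n]}, where p is the partial correlation of weeks 7 and 14 given baseline: p = (r − r²)/(1 − r²) = 0.24/0.64 = 0.375, so p² = 0.141.
- m = 2: √(0.115 + 0.859) = 0.987.
- m = 5: √(0.090 + 0.859) = 0.975.
- m = 10: √(0.067 + 0.859) = 0.962.

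**(c) Excluded children with baseline only, or week 14 added for children who already have baseline and week 7.** The ratio is 1.000: no gain.

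**Check with the covariance estimated.** The formulas treat the covariance as known. A simulation with REML, unstructured 3×3 covariance, common baseline mean, r = 0.6, 9 complete per arm and 400 replicates gave these ratios of empirical spread:

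| The 10 excluded per arm have | Ratio |
|---|---|
| baseline only | 1.000 |
| baseline and week 14 | 0.991 |
| weeks 7 and 14, no baseline (5); baseline only (5) | 0.838 |
| weeks 7 and 14, no baseline (all 10) | 0.770 |

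If each form is instead missing independently in 31% (0.69² × 38 ≈ 18 complete), the spread ratio with estimated covariance was 0.885 at r = 0.5 and 0.857 at r = 0.7, a reduction of about 11–14%.

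**Uncorrected standard errors mislead here.** In the baseline-only case the mean REML standard error was 0.356 against 0.378 for ANCOVA, although the true spread was identical. In the second row it was 0.345 against 0.387, an apparent gain of 11% where the true gain was about 1%.

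**Scale in power terms.** With unit SD the ANCOVA standard error is √(2 × 0.64/9) = 0.377. At d = 0.68, two-sided 0.05 and the normal approximation, power is about 44% with complete cases, 49% with m = 2 and 56% with m = 5 in case (a). The sidedness of the ANCOVA is not stated in the plan. These figures show scale only.

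**The case against.** The strongest objection is that no gain is guaranteed. Nothing in the documents shows that any child has week 7 without baseline. Section 14 places consent and baseline assessment together in recruitment, so loss of later forms is more natural than heavy baseline loss. The 31% pattern would also leave only about 0.69³ × 38 ≈ 12.5 children with all three forms, which is hard to square with the 32 in 5.2. This stands: the benefit is conditional, and the zero case is a real possibility.

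A reader might infer gains of 16–20% from the 31% pattern, or 6–7% if only week 7 (53%) and week 14 (31%) are missing. Simulations with a known covariance give those values, but they compare a model that knows the slope with an ANCOVA that estimates it from about 18 children. With week 14 removed altogether from the second pattern, the same comparison still shows ratios of 0.955–0.963, a gain of about 4% where none exists. The supportable sizes are 11–14% and 1–4%.

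A reader might also infer that listwise deletion needs the stronger missing-data assumption. That is not generally true. Complete-case ANCOVA is valid if missingness depends only on arm and baseline, even where baseline is missing because of its own value. The likelihood model needs missingness at random given the observed scores, which that case violates, but it lets a missing week 7 depend on week 14 as well. Neither is uniformly weaker.

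Finally, 5.2, 8.1 and 8.3 report realised counts, effect sizes and post-hoc power, so a change now may follow sight of outcomes. That governs how the change is labelled. It does not make listwise deletion the better estimator.

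**Conclusion.** The point holds as a conditional loss of precision. The rule does discard observed week-7 outcomes whenever baseline is absent, and the week-7 analysis uses no week-14 score. With 9 complete children per arm and r = 0.6, recovering them reduces the standard error by about 6% (2 per arm) or 14% (5 per arm) for children with week 7 but no baseline. For children with baseline and week 14 but no week 7 it is about 1–4%, and for children with baseline only it is zero. Which case applies cannot be read from the documents.

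The documents do not support a claim that all 19–21 excluded children are recoverable, or that the planned ANCOVA is biased. The gap between 17–19 analysed and the 32 in 5.2 does not settle the pattern either, since 5.2 does not say which measures and visits count as complete. Where nothing can be recovered, the constrained model essentially matches ANCOVA, so little is risked provided the small-sample correction is used.

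**What to change.** For the standardised measures only, in 8.2.1 and 8.3:

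- Report missingness by arm, visit and measure.
- Replace listwise deletion with a baseline-constrained repeated-measures model: the three visits as outcomes, a common baseline mean, arm × visit terms at weeks 7 and 14, unstructured covariance, Kenward-Roger correction, and the week-7 arm contrast as the primary estimate. The separate week-14 term is needed because IG2 has also received the programme by then.
- Include every randomised child with any score.
- If the model does not converge for a scale, use ANCOVA with mean-imputed baseline and a missing-baseline indicator. In a check of this fallback the standard error fell by 7–14% with each form missing in 31%, and by 0% when no baseline was missing.
- State what becomes of the maturation covariate in 8.2.1. The waitlist arm's visit means already carry the average change over the waiting period.
- Report the complete-case ANCOVA alongside.
- If outcome data have already been analysed, label the change as post hoc.

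The cost is SAP wording, standard software and slightly more analysis work, with no new data. The small-sample correction is essential at this size; without it part of the apparent gain is false.

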8.4 Significance Level

Alpha set at 0.05 for all analyses

9. Data Management

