7.1 Primary Outcome Measures

7.1.1 Standardized Assessment Battery

NIH Toolbox Parent Report Emotion Measures:

- Negative Affect subdomain (anger, fear, sadness/depression)
- Psychological Well-being subdomain (positive affect, life satisfaction)

PROMIS Early Childhood Measures:

- Flexibility
- Persistence (Note: Curiosity and Frustration Tolerance removed due to ceiling effects)

Pediatric Quality of Life Inventory (PedsQL):

- Physical Functioning
- Emotional Functioning
- Social Functioning
- School Functioning

- Composite Score

Canadian Occupational Performance Measure (COPM):

- Parent proxy report of child's occupational performance
- Used primarily for Goal Attainment Scaling development

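### Every week-7 standardized score is a primary efficacy test at 0.05 with no ranking or adjustment, so the chance of at least one false-positive result is about 20-46% (assumed correlation 0.7 to 0)

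*Combined protocol and SAP*

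**What the plan says.** The heading "7.1 Primary Outcome Measures" covers everything in section 7; there is no secondary list. Under it stand:

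- NIH Toolbox: "Negative Affect subdomain (anger, fear, sadness/depression") and "Psychological Well-being subdomain (positive affect, life satisfaction")
- PROMIS: Flexibility and Persistence
- PedsQL: four subscales and a composite
- COPM, described as "Used primarily for Goal Attainment Scaling development"
- GAS: three domains

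Section 8.2.1 defines the primary efficacy ANCOVA, IG1 against the IG2 waitlist, with "Dependent Variables: Week 7 standardized assessment scores". No score is singled out.

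Section 8.2.2 defines a second primary efficacy ANCOVA, on GAS, and adds: "Combined score calculated by averaging three domain T-scores". Its comparison is IG1 in weeks 0-7 against IG2 in weeks 7-14.

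The only statement on error control is in section 8.4: "Alpha set at 0.05 for all analyses". The plan gives no order of testing, no adjustment and no rule for when the trial counts as positive.

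**The concern.** When many outcomes are all primary and each is tested at 0.05, the 5% level holds for each test separately and not for the set. If BRP does nothing, a significant result somewhere in the battery is much more likely than 5%, and the plan has no rule that tells such a result from a prespecified finding.

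This matters here because section 15.1 plans to publish primary efficacy results, and section 8.1 already reports effect sizes for just three measures (PROMIS Flexibility, PROMIS Persistence and PedsQL Social Functioning). Without a stated order, a reader cannot tell whether these three were of prior interest or were the largest of about ten. With 8-10 children per group (section 8.3), estimates are noisy and a lone small p-value is weak evidence.

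**Working it through.** The plan states no family-wise error rate, so there is no figure of its own to reproduce. Its only input is 0.05 per analysis (section 8.4).

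**Step 1. Count the tests of BRP against control (sections 7.1.1 and 8.2.1).**

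- NIH Toolbox: 2 subdomains, or 5 scales (3 + 2)
- PROMIS: 2
- PedsQL: 4 subscales + 1 composite = 5
- Total without COPM: 2 + 2 + 5 = 9, or 5 + 2 + 5 = 12

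**Step 2. Assumptions.** The ANCOVA is two-sided: section 8.2.1 states one-tailed tests only for the secondary paired comparisons. The documents give no correlations between outcomes, so a common correlation of 0, 0.5 and 0.7 is used.

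**Step 3. Independent tests, no effect.**

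- Either direction, 1 - 0.95^k: 1 - 0.95^9 = 0.370; 1 - 0.95^12 = 0.460
- Beneficial direction only, 1 - 0.975^k: 1 - 0.975^9 = 0.204; 1 - 0.975^12 = 0.262

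**Step 4. Correlated tests** (simulated equicorrelated normal statistics, 400,000 draws).

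| Correlation | Either direction, 9 to 12 tests | Beneficial only, 9 to 12 tests |
|---|---|---|
| 0 | 37-46% | 20-26% |
| 0.5 | 27-32% | 13-16% |
| 0.7 | 20-23% | 10-12% |
| 0.8 | 17-19% | 8-9% |

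If the ANCOVA were one-sided at 0.05, the beneficial figures would be 37-46% at correlation 0 and 18-20% at 0.7. The expected number of false positives is 9 × 0.05 = 0.45 to 12 × 0.05 = 0.60 (two-sided), whatever the correlation.

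**Step 5. Add COPM and GAS.** One COPM test and four GAS tests (three domains and their average) give 14 to 17. At correlation 0.7, 14 tests give 25%. If independent, 17 tests give 1 - 0.95^17 = 0.582.

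**Step 6. What the GAS test compares.** Under section 4.2, IG1 receives BRP in the first 7 weeks and IG2 in the second. Section 8.2.2 compares exactly those two periods, so both sides are treated. A difference there is not evidence for BRP against no BRP.

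**Step 7. Price of adjustment.** Take a two-sided, two-sample t-test at d = 0.68 (section 8.1) with 8 + 9 to 9 + 10 children (the 17-19 of section 8.3). Power is 26-29% at 0.05. At 0.05/9 = 0.0056 it is 6-7%, and at 0.05/12 = 0.0042 it is 5-6%. At 0.05/8 = 0.00625, the first Holm step for the list proposed below, it is 7-8%. A baseline covariate would raise all of these by an amount that the documents do not allow one to compute.

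**The case against.** The best defence is that section 8.1 calls this a pilot limited by the centre's enrolment, that section 8.2.1 asks for effect sizes with 95% confidence intervals, and that the plan never claims 5% overall. All three are true. They support an exploratory reading, but the plan does not adopt one: it states directional hypotheses (section 2.2) and uses the primary efficacy label. Section 2.2 could also be read as requiring improvement in every domain, which would need no adjustment, but no such success rule is stated.

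A reader might infer a stronger claim: that the chance of a false efficacy claim is 25-58%. The documents do not support that.

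- The figure counts errors in either direction, including IG1 doing worse.
- The upper end needs 17 independent tests. That is impossible, because the PedsQL composite and the GAS average are built from their own components; allowing for this gives about 56% at most.
- It counts COPM, which the plan treats mainly as a goal-setting tool, and four GAS tests that compare treated with treated. Section 8.2.2 does not clearly specify four: between one and four can be read.
- The lower end rests on an assumed correlation of about 0.7 and is not a floor.

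Nor should a significant result be called the likely chance outcome: at correlations of 0.5 or 0.7, no false positive is more likely than one. That any single result may be announced as efficacy is inferred from the absence of a rule; section 15.1 does not say it.

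**Conclusion.** The gap is real and should be fixed. For the standardized battery alone, the chance under no effect of at least one p<0.05 is 37-46% if tests are independent, 27-32% at correlation 0.5 and 20-23% at 0.7. In the beneficial direction only it is 20-26%, 13-16% and 10-12%. These rest on 9-12 two-sided tests and assumed correlations. The independent figures are upper limits, because the PedsQL composite overlaps its subscales. Every case computed exceeds 5%. The wider 25-58% should not be quoted as a rate of false efficacy claims. Caregiver outcomes, which are also primary objectives (section 2.1), are not counted, because sections 7 and 8 name no test for them.

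**What to change.** In section 8.4:

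1. Apply Holm at 0.05 to the week-7 IG1-against-IG2 ANCOVAs over one fixed list of eight: the 2 NIH Toolbox subdomains, 2 PROMIS scales and 4 PedsQL subscales. Thresholds run from 0.05/8 = 0.00625 up to 0.05. Holm holds the family-wise rate at or below 5% under any correlation.
2. Report the PedsQL composite and the single NIH Toolbox scales descriptively.
3. Take COPM out of the tested outcomes. Report the GAS ANCOVA and the secondary paired tests as descriptive, not as primary efficacy.
4. Give unadjusted estimates with 95% confidence intervals beside the Holm-adjusted p-values, and state the number of tests.
5. Say that the adjustment was added after data were seen. A full fixed list avoids picking one favoured scale now. It cannot undo earlier selection: section 7.1.1 notes that two PROMIS scales were dropped for ceiling effects.

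If the sponsor prefers no adjustment because this is a pilot, drop the primary efficacy wording throughout and label all results exploratory.

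The work is SAP text and recalculated p-values; no data collection changes. The downside is power: at d = 0.68, from about 26-29% at 0.05 to about 7-8% at the first Holm step. Few adjusted results are likely to reach significance, and the estimates and intervals will carry most of the information.
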